
## **7. PLANNED ANALYSIS**

Disposition of the patient population participating in the trial will be analysed as follows:

- Open-label ramipril run-in disposition will be summarized using the screened patients set
- Double-blind disposition will be summarized by treatment using the randomized set (no “Total” column)
- Double-blind disposition per period will also be summarized by treatment sequence using the randomized set ( “Total” column will be included).

Disposition summaries by region, country and site are not applicable for this single-centre trial.

IPDs during the randomized treatment period will be listed only.

The frequency of patients in different analysis sets will be summarised in total, and by treatment sequence.

For in-text tables presenting descriptive analysis of the endpoints and other variables (analysed on original scale), the set of summary statistics is: N (number of patients with non-missing values), mean, standard deviation (SD).

For end-of-text and appendix tables, the set of summary statistics is: N (number of patients with non-missing values), mean, SD, min, Q1 (lower quartile), median, Q3 (upper quartile), max.

For the in-text, end-of-text and appendix tables presenting descriptive analysis of the endpoints and other variables (analysed on logarithmic scale), the respective summary statistics (e.g. gMean, gCV, etc.) will be used.

Statistical parameters will be displayed to a defined number of decimal places as specified in the BI guideline "Reporting of Clinical Trials and Project Summaries" (3)

Tabulations of frequencies for categorical data will include all possible categories and will display the number of observations in a category as well as the percentage (%) relative to the respective treatment or treatment sequence (as applicable and unless otherwise specified; all patients in the respective patient set whether they have non-missing values or not).

Percentages will be rounded to one decimal place. The category missing will be displayed only if there are actually missing values.

### **7.1 DEMOGRAPHIC AND OTHER BASELINE CHARACTERISTICS**

Descriptive summaries of the following demographic variables, as measured at screening, will be presented:

Table 7.1: 1 List of demographic variables at screening and their categorisation

Demographic variable at screening	FAS	RIS
Sex	X	X
Race	X	X
Ethnicity	X	X
Age (year)	X	X
*Age categories (18 to 23, 24 to 28, ≥29 years)	X	X
*BMI categories (<25, 25 to <30, ≥30 kg/m  )	X	X
Height (cm)	X	X
Smoking history	X	X
Alcohol status	X	X
Time since diagnosis of diabetes (year)	X	X
*Time since diagnosis of diabetes (≤5, >5 to ≤10, >10 to ≤25, >25 year)	X	X
eGFR	X	X
*eGFR categories (75 to ≤115, 115 to ≤125, 125 to ≤140 mL/min/1.73m  )	X	X
UACR (mg/g)	X	X

By treatment sequence and Total

\*Definitions of categories are subject to change.

Descriptive summaries of the following variables measured at screening baseline (visit 4) will be presented:

Table 7.1: 2 List of baseline characteristic variables at screening and their categorisation

Baseline characteristics at screening	FAS	RIS
GFR (mL/min/1.73m  )	X	X
*GFR categories (≤115, >115 mL/min/1.73m  )	X	X
HbA1c (%)	X	X
*HbA1c categories (<8.5, ≥8.5%)	X	X
FPG (mg/dL)	X	X
*FPG categories (<54, 54 to ≤70, 70 to ≤126, 126 to ≤140, 140 to <200, ≥200 mg/dL)	X	X
Weight (kg)	X	X
*Weight categories (≤50, >50 to ≤70, 70 to ≤90, >90 kg)	X	X
Waist circumference (cm)	X	X
Systolic blood pressure (bpm)	X	X
Diastolic blood pressure (bpm)	X	X
*Blood pressure categories (SBP≥140 or DBP≥90, SBP<140 and DBP<90)	X	X

By treatment sequence and Total

\*Definitions of categories are subject to change.

The table on baseline characteristics at screening ([Table 7.1: 2](#)) will be reproduced for randomization baseline, even though the randomization baseline for the continuous part of these variables will also be presented together with the respective further endpoint.

Categories for baseline characteristics are defined in [Section 6.4](#).

## 7.2 CONCOMITANT DISEASES AND MEDICATION

Concomitant medication use will be summarised by Anatomical-Therapeutic-Chemical classification level 3 (ATC3) and preferred name.

Descriptive summaries of concomitant medication will be presented for:

- Screening period (Pre-treatment) for the RIS; by OL ramipril
- Run-in period for the RIS; by OL ramipril
- Run-in period for the FAS; by treatment sequence and “Total”
- Double-blind treatment (including washout) for the FAS; by treatment sequence and “Total”
- Double-blind treatment (excluding washout) for the FAS; by treatment.

Separate summaries of use of antihypertensives, ASA or lipid lowering drugs will be presented:

- At screening baseline for the RIS
- At randomisation baseline for the FAS; by treatment sequence and “Total”

The displayed categories and defining ATC levels and ATC codes are shown in [Table 9.2: 1](#).

Background pre-existing insulin therapy, including a categorisation of patients using MDI versus CSII will be presented for the RIS.

Background total daily insulin dose at screening baseline and randomisation baseline respectively will be presented in a summary table in insulin 'unit' and 'units/kg' as units of insulin per kg body weight at baseline. The table will also display the total daily basal insulin dose and the total daily bolus insulin dose at the relevant baseline. The number of insulin injections at the relevant baseline will be presented for multiple daily injection (MDI) patients. These tables will be presented for the RIS and FAS, by treatment sequence and “Total” respectively.

Total daily ramipril dose at the start of the open-label ramipril run-in is assumed to be 5mg from the data captured (that is, the protocol-specified initial dose 5mg qd), and so will not be summarized.

Total daily ramipril dose prior to the start of the double-blind treatment period will be summarized for the FAS, by treatment sequence and “Total”.

Total daily ramipril dose prior to the start of each treatment crossover period will be summarized for the FAS, by treatment.

Concomitant diseases will be summarised by MedDRA System Organ Class (SOC) and preferred term (PT). Both concomitant diseases and relevant diabetic medical history will be presented for the RIS and for the FAS, by treatment sequence and “Total” respectively.

### **7.3 TREATMENT COMPLIANCE**

Only descriptive statistics are planned for this section of the report.

Frequency distribution of patients with an overall open-label ramipril compliance between 80% and 120% (inclusive) will be reported for the RIS, as well as the patients outside this range. Overall compliance for this purpose will be calculated as a weighted average of reported OL ramipril compliance (from Visits 5 and 8 on the eCRF).

Frequency distribution of patients with an overall double-blind ramipril compliance between 80% and 120% (inclusive) will be reported for the FAS, by treatment sequence, as well as the patients outside this range. Overall compliance for this purpose will be calculated as a weighted average of reported DB ramipril compliance (from Visits 11, 12 and 15 on the eCRF).

It is also noted that ramipril dose may change throughout the trial, and therefore the recorded ramipril compliance on the eCRF needs to take account of this. Since this is handled using the compliance worksheet and instructions given to the site, further details are not given here.

Frequency distribution of patients with a double-blind empagliflozin/placebo compliance between 80% and 120% (inclusive) will be reported for the FAS, by treatment, as well as the patients outside this range. Since a single compliance value is recorded on the eCRF at the end of each treatment crossover period (Visit 11/EoT and Visit 15/EoT respectively), this single value will be used. No weighted average needs to be calculated.

In the above, where an overall compliance is calculated from more than one visit, if compliance is missing at more than one of these visits, then overall compliance will be set to missing.

### **7.4 PRIMARY ENDPOINT**

The primary endpoint in this trial is GFR measured after 4 weeks of double-blind treatment with either empagliflozin or placebo.

#### **7.4.1 Primary analysis of the primary endpoint**

The protocol planned primary analysis of the primary endpoint in this early terminated trial cannot be performed, because data are too sparse in the predefined subgroup of hyperfilterers.

#### **7.4.2 Sensitivity analysis, subgroup analysis, exploratory analysis of the primary endpoint**

The primary endpoint will be analysed on all patients in the FAS, only. This was a predefined secondary analysis of the primary endpoint according to the protocol. No further sensitivity

analyses are planned. The plan for the analysis of the primary endpoint by subgroups are outlined in [Section 7.9](#).

#### 7.4.2.1 Random effects crossover model MMRM1

This predefined secondary analysis of the primary endpoint is analogous to the CTP predefined primary analysis of the primary endpoint on the subgroup of hyperfilterers, now removed, but just on all patients in the FAS. The aim of this analysis is to investigate the treatment effect, whilst adjusting for baseline GFR.

This is a random effects crossover model, which is a Mixed-Effects Model for Repeated Measures (MMRM) for a crossover design using restricted maximum likelihood (REML). The model is as described in the CTP Section 7.3.1.1 with a random effect for patient, fixed effects for the class variables treatment and period, and a fixed effect for the continuous variable randomisation baseline GFR. For ease of terminology, it will be referred to as MMRM1. The model structure also gives rise to an implicit compound symmetry covariance structure for between patient variance, and consequently within patient and between patient variance is assumed to be independent under this model.

The Kenward-Roger approximation will be used to estimate denominator degrees of freedom and adjust standard errors. Significance tests will be based on least-squares means using a two-sided  $\alpha = 0.050$  (two-sided 95% confidence intervals). The residuals are assumed to have a multivariate normal distribution with zero means and covariance matrix of the type specified above.

The primary treatment comparison will be the least squares mean contrast between treatments (empagliflozin minus placebo). The treatment contrast, its two-sided 95 % confidence interval and its p-value will be reported. The model predicted GFR values for each of the baseline GFR values and treatment will be presented graphically. Descriptive tables of the GFR values by period and treatment and condensed over the two treatment periods will be presented. Baseline and change from baseline will be included in the summary.

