### *Primary endpoint analysis*

Analyses on subgroups of GFR hyperfilterers (n=2), GFR responder (n=2) and GFR non-responder (n=0) groups are not possible because there are too few patients per group. Therefore, it is not possible to test the null hypothesis of the study.

Subsequently, no per protocol set (PPS) will be determined, however, the important protocol deviations will still be identified prior to unblinding.

The subgroup of normofilterers (n=29) is very similar to the overall set of patients in the full analysis set (FAS) (n=31) and therefore, only the overall set of patients will be analysed.

For the overall set of patients, all pre-specified analyses will be implemented, except for the pre-specified analysis using screening GFR and the screening GFR by treatment interaction. Due to the high correlation between screening GFR and baseline (pre-randomisation) GFR, it is expected that this would lead to similar findings, compared to the analysis (with interaction) using pre-randomisation GFR as baseline.

The assumptions behind the models will be investigated by way of model diagnostics and the potential period effect by graphics. Otherwise, the analyses will be as per protocol.

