### **6.6.1 Efficacy analysis**

If one of the pair of scheduled GFR measurements (or other similarly recorded data) is missing, the endpoint will be defined as the single remaining non-missing value, as specified in [Section 5.1](#). If both of the scheduled GFR measurements (or other similarly recorded data) are missing, then the endpoint is missing at that visit.

All GFR measurements available on the trial database after data cleaning activities have been completed (or other similarly recorded data) will be assumed to be technically plausible and eligible for use in the analysis, i.e. will not be set to missing programmatically in any cases.

In the event that GFR values (or other similarly recorded data) at a particular visit are outside the relevant visit window specified in [Section 6.7](#), the values will be retained in analysis datasets, but not used in any analysis.

In the event that randomisation baseline GFR is missing, or **both** double-blind treatment period GFR values are missing, such a patient will be excluded from the FAS by definition, and therefore, excluded from all analyses of GFR after 4 weeks of double-blind treatment. Since ramipril is given to lower GFR in the run-in period, under no circumstances will a missing randomisation baseline GFR be imputed by screening baseline GFR, if randomisation baseline GFR is missing after data cleaning activities have been completed.

For all continuous endpoints (including GFR after 4 weeks of double-blind treatment), any patient with only one available value will still be included in the mixed model analyses in which patient is fitted as a random effect (including the primary analysis of GFR). Missing data for one of the crossover periods is implicitly handled in this type of statistical model under the missing at random (MAR) assumption. This also means that all patients in the FAS will be included in the primary analysis of the primary endpoint. Such a patient will be excluded from other analyses in which patient is fitted as a fixed effect. If it is the first crossover period where the missing value occurs, such a patient will also be excluded from any analysis which only uses data from the first double-blind treatment period.

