#### 7.4.2.3 Random effects crossover model on the natural logarithmic scale MMRM3

The primary analysis as described in [Section 7.4.2.1](#), will be repeated on all patients in the FAS with the modification that all GFR measurements (endpoint and randomisation baseline values) will be replaced by their natural logarithms (loge). Estimates from this model will be back-transformed and the estimate of the treatment effect reported as the ratio of geometric means for GFR (empagliflozin/placebo), together with its 95% CI and nominal p-value. A value of less than 1 for the ratio of geometric means therefore represents a lower mean GFR on empagliflozin compared to placebo.

For ease of reference, this will be referred to as MMRM3.

In order to examine the treatment effect, the same graphical displays (scatter plot and boxplot) as defined in [Section 7.4.2.1.3](#) will also be produced on the natural log scale.

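### Does the SAP give the all-patient GFR model (MMRM1) a confirmatory status that the rest of the plan denies it?

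*SAP*

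**What the plan says.** Four places settle what can still be tested.

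- Section 4, under the primary endpoint analysis, gives 2 hyperfilterers, 2 responders, no non-responders and 29 normofilterers. It concludes: "Therefore, it is not possible to test the null hypothesis of the study".
- Section 7.4.1 says the planned primary analysis "cannot be performed, because data are too sparse in the predefined subgroup of hyperfilterers".
- Table 6.3: 1 enters the FAS under secondary analyses for both the primary and the secondary endpoint.
- Section 7.4.2, whose heading covers sensitivity, subgroup and exploratory analyses, says of the FAS analysis: "This was a predefined secondary analysis of the primary endpoint according to the protocol". The first sentence of 7.4.2.1 repeats that status for MMRM1.

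Other wording points the opposite way.

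- Section 7.4.2.1: "Significance tests will be based on least-squares means using a two-sided" alpha of 0.050, paired with two-sided 95% intervals.
- Same section: "The primary treatment comparison will be the least squares mean contrast between treatments (empagliflozin minus placebo", and then "confidence interval and its p-value will be reported", with no qualifier on the p-value.
- Section 6.6.1, on missing data: "all patients in the FAS will be included in the primary analysis of the primary endpoint".
- Section 7.4.2.3, introducing the log-scale model MMRM3: "The primary analysis as described in" Section 7.4.2.1.

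The p-values of MMRM2 (7.4.2.2), MMRM3 (7.4.2.3) and McNemar's test (7.5.2.2) are called nominal, and those of the subgroup model MMRMSG (7.9) descriptive. The general caveat in 5.2.2 that p-values are descriptive is written for the secondary endpoint only.

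**The concern.** One analysis appears to carry two inferential statuses. The plan says that the study hypothesis, which concerned hyperfilterers, is out of reach, and then keeps a test at a stated alpha for a model that it elsewhere calls primary. Of the five GFR analyses with a stated p-value in the text available, MMRM1 is the only one without a nominal or descriptive label. A reader could infer that its p-value was meant to count for more than the others.

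What would be at stake is the claim, not the estimate. If p<0.05 from MMRM1 were reported as a significant result of the primary analysis, it would suggest that the trial had answered its question about hyperfilterers, when 29 of the 31 patients are normofilterers.

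**Working it through.** **1. Is the stated alpha right?** Section 7.4.2.1 pairs a two-sided alpha of 0.050 with a two-sided 95% interval. 1 - 0.95 = 0.05, so the two agree and there is no numerical error.

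**2. Whom does MMRM1 describe?** The counts come from Section 4.

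- 29 + 2 = 31.
- Hyperfilterers: 2/31 = 6.5%. Normofilterers: 29/31 = 93.5%.

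With complete pairs, the MMRM1 treatment contrast gives each patient's own treatment difference a weight of 1/(2 x size of that patient's sequence). The SAP does not give the sequence split, so a range is assumed.

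| Assumed split | Weight of 2 patients in the larger sequence | Weight of 2 patients in the smaller sequence |
|---|---|---|
| 16/15 | 2/32 = 6.3% | 2/30 = 6.7% |
| 17/14 | 2/34 = 5.9% | 2/28 = 7.1% |
| 18/13 | 2/36 = 5.6% | 2/26 = 7.7% |

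If the effect in hyperfilterers differed from the rest by an assumed 10 mL/min/1.73m², the contrast would move by 10 x 0.0625 = 0.6 to 10 x 0.0667 = 0.7 for the 16/15 split, and by 0.6 to 0.8 for 18/13. MMRM1 is therefore almost wholly a statement about normofilterers. That describes the population mix, which Section 4 discloses. It does not measure an error in the plan.

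**3. What does the alpha sentence do?** It stands beside the Kenward-Roger method and the residual assumptions, and its parenthesis ties alpha to the interval level. Section 7.4.2.2 takes over the model and assumptions of 7.4.2.1 for MMRM2, and 7.4.2.3 repeats the 7.4.2.1 analysis on logarithms for MMRM3. Both p-values are called nominal. The same specification thus sits beside nominal p-values without conflict, so the sentence fixes a computation and an interval level and does not confer confirmatory standing.

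**4. Which hypothesis is tested?** Section 4 makes its remark about the null hypothesis because the filtration subgroups are too small. It does not say that nothing may be tested in the FAS. No treatment effect in the FAS is a different hypothesis, and MMRM1 tests it in a predefined population.

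**5. How strong are the stray labels?**

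- Section 7.4.2.3 points directly to 7.4.2.1, so its label does contradict 7.4.2 and 7.4.2.1.
- Section 6.6.1 is a missing-data rule and does not name MMRM1. It also provides for analyses with patient as a fixed effect, and none appears in the text available. It reads as carried-over wording.
- The term primary treatment comparison in 7.4.2.1 names the main contrast within the model, not the rank of the model.

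**6. What would relabelling change?** The model, FAS, estimate, interval and p-value would all stay the same.

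**The case for a change.** The best argument for a change is that the status of a p-value should be fixed before unblinding and not left to the report author. Section 7.4.2.1 is not simply untouched text: it was adapted to say that the hyperfilterer analysis was removed, yet the significance-test sentence was kept. MMRM3 is MMRM1 on the log scale, and its p-value is nominal while that of the parent model is unmarked. The caveat in 5.2.2 does not reach MMRM1. A careful reader can resolve the conflict, but a plan should not need one.

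Part of this stands. The label in 7.4.2.3 is wrong against 7.4.2 and 7.4.2.1, the same label survives in 6.6.1, and the missing qualifier in 7.4.2.1 is out of step with the other GFR analyses.

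The feared consequence does not stand. To report MMRM1 as a positive primary analysis, an author would have to set aside Section 4, Section 7.4.1, Table 6.3: 1, Section 7.4.2 and the first sentence of the very section that specifies the model. The status is therefore already fixed in the plan. Nor is there much for a wider caveat to cover, since the other four p-values already carry a nominal or descriptive label.

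**Conclusion.** No change to the plan follows. The inconsistency is clerical: one label in 7.4.2.3 that contradicts its own cross-reference, one carried over in 6.6.1, and one missing qualifier in 7.4.2.1. Followed as written, the plan yields a correctly sized test in a predefined population, and the sections that govern its status direct that it be reported as secondary. The effect of the slip on any estimate, interval or p-value is nil.

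The weights of 5.6% to 7.7% for the two hyperfilterers rest on complete pairs and an assumed sequence split, and the conclusion does not depend on them. The protocol is not available, so what it says on the status of p-values from secondary analyses could not be checked. The SAP settles the point on its own text.

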##### 7.4.2.1.1 Model diagnostics

Model diagnostics will be limited and based on a standard investigation of the studentized residuals.

##### 7.4.2.1.2 Examination of potential period effect

The potential period effect will be examined graphically. Firstly, presenting the mean GFR on the y-axis against the period on the x-axis, split by treatment and each of the treatments joined by a line. Secondly, the within patient differences will be examined by individual patient profiles, one for each treatment sequence. Each plot will present the GFR on the y-axis versus the period on the x-axis (patients joined from period 1 to period 2) and the mean GFR at each period superimposed.

##### 7.4.2.1.3 Examination of treatment effect

To investigate the treatment effect graphically, a scatter plot will be produced, displaying one treatment on the y-axis versus the other treatment on the x-axis, including a 45-degree line

and the mean of the two treatments superimposed. In addition, a boxplot showing the distribution of the GFR at week 4 by treatment will be included.

#### 7.4.2.1.4 Examination of relationship between GFR at baseline and week 4, by treatment

To investigate the relationship between baseline GFR and GFR at week 4, by treatment, there will be a scatter plot with GFR at week 4 on the y-axis and baseline GFR on the x-axis using different symbols for each of the two treatments. In addition, GFR at week 4 will be presented by subgroups of GFR at baseline, split into three approximately equally sized groups (<107, ≥107 to <120, ≥120) using boxplots with one display per treatment group. The overall GFR (irrespective of baseline) will also be included.

